10.6 PRIMARY SAFETY ANALYSIS

10.6.1 Primary Safety Hypothesis

The primary safety hypothesis to be tested is that the rate of Major Adverse Events (MAEs) at 30 days in the study population is less than 56%, which is the rate of MAE at 30 days in the Society for Vascular Surgery (SVS) open surgery group. MAEs include all-cause death, bowel ischemia, myocardial infarction, paraplegia, renal failure, respiratory failure, stroke, and procedural blood loss $\geq 1,000\text{mL}$. The hypothesis test will be evaluated by the exact test as a one-tailed test, using significance level $\alpha=0.025$. Multivariable analyses will be used to assess predictors of success. The null and alternative hypotheses are provided below.

$$H_0: P_t \geq 0.56 \text{ vs. } H_1: P_t < 0.56,$$

where P_t is the MAE rate at 30 days in the study test group.

10.6.2 Sample Size

The primary trial safety variable is the rate of MAEs (as defined previously) at 30 days following treatment with the Nellix System. The SVS open surgical group has been characterized.[†]

Owing to the availability of data within the SVS database for this surgical group, it is reasonable to consider it for sample size generation for the safety endpoint. The MAE rate in the SVS surgical control group at 30 days is 56%. This is reasonably conservative as a performance goal. To this point, a recent publication finds that the rates of these major adverse events are similar between open infrarenal aneurysm repair and open repair of juxtarenal aneurysms and those involving the renal arteries), with the exception of bleeding and renal events, which were significantly higher with open more complex aneurysm repair.[‡] To be further conservative and to account for the fact that in the present study, shorter necked infrarenal aneurysms will be treated endovascularly with the Nellix System, the rate for the test arm has been increased to 16.6%. It is expected that the rate of MAEs within 30 days in this study will be smaller than

*Fleiss, J. The statistical basis of meta-analysis. *Statistical Methods in Medical Research* 1993;2:121-45.

Confidential. This document and the information contained herein may not be reproduced, used or disclosed without written permission from Endologix, Inc.

that of the SVS historical surgical control group as noted above. The sample size for this trial is calculated to demonstrate a difference between the observed MAE rate and the performance goal established using SVS historical surgical data.

If we assume that $P_t = 0.166$, $P_c = 0.560$, one-sided alpha = 0.025, and power = 80%, a very small number of subjects are required in the treatment group to test the above hypothesis. Should the Nellix rate be as high as 31%, then 50 subjects would provide approximately 81% power to test the primary safety endpoint at the one-sided 2.5% significance level.

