10.6.3 Analysis Plan

All subjects who receive treatment will be included in the safety analysis.

A univariate test will be done with the exact binomial distribution to determine if the frequency of MAE in the study population is statistically significantly less than 0.56. The formula for this test is provided below.

$$P(X \leq x_t | 0.56) = \sum_{k=1}^{x_t} \binom{n_t}{k} 0.56^k 0.44^{n_t-k} < 0.025$$

Where x_t is the number of study subjects experiencing an MAE and n_t is the number of subjects in the study. If the above expression holds for the observed x_t , the null hypothesis will be rejected and the alternative hypothesis will be accepted.

If there is heterogeneity among the study sites in MAE response, the analysis will be done by the method of Fleiss (1993). The test statistic will be given by the following formula.

$$z = \frac{(\bar{p}_T - 0.56)}{SE(\bar{p}_T)}$$

Where the formula for the weighted estimate of the proportion is given by the following:

$$\bar{p}_T = \frac{\sum_k W_k p_{Tk}}{\sum_k W_k}$$

And the formula for the weight in site k is given by the following:

$$W_k = \left(\frac{1}{n_k} p_k (1 - p_k) \right)^{-1}$$

And the formula for the standard error is given by the following:

$$SE(\bar{p}_T) = \left(\sum_{k=1}^{m_T} W_{Tk} \right)^{-1/2}$$

If the z has a P-value less than a one-sided alpha of 0.025, the null hypothesis will be rejected and the alternative will be accepted.

To determine those factors that may be associated with MAE, a supportive covariate analyses will be performed by logistic regression to determine if there are differences in the rates among groups when adjusted for other factors in the study population only. Covariates for these analyses will be age, gender, ASA class, cardiac/coronary artery disease (a composite variable to include arrhythmia, CHF, prior MI, CABG/PCI, heart valve repair/replacement), histories of cancer, cerebrovascular accident, coagulopathy, COPD, diabetes, hypertension, liver disease, peripheral arterial occlusive disease, renal failure, smoking, maximum aneurysm diameter, and study site. The final model will be reduced by backward elimination until no covariate terms remain in the model with a P-value less than 0.05.

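### Section 10.6.2 gives about 81% safety power for 50 subjects at a 31% MAE rate, but the plan's own exact test gives 93.4%; the error is conservative and minor

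*Combined protocol and SAP*

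**What the plan says.** Section 10.6.1 of the combined protocol and SAP sets a single-arm hypothesis: the null is a 30-day MAE rate of 56% or more, the alternative a lower rate. The test is exact and one-tailed, at a significance level of 0.025. The Analysis Plan in 10.6.3 confirms the method ("A univariate test will be done with the exact binomial distribution to determine if the frequency of MAE" is below 0.56) and prints the binomial tail sum with 0.56 and 0.44 as fixed probabilities.

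Section 10.6.2 (Sample Size) makes two statements about safety power. At the planning rate of 16.6% ("one-sided alpha = 0.025, and power = 80"%), it says that "a very small number of subjects are required in the treatment group". It then takes a less favourable case, "Should the Nellix rate be as high as 31"%, and says that "then 50 subjects would provide approximately 81% power to test the primary safety endpoint at the one-sided 2.5% significance level".

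Section 10.7.2 takes the trial size from effectiveness, as the larger of the two sample sizes: 132 evaluable subjects, recruited as 132/0.88 = 150.

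**The concern.** The 81% sentence comes with every input needed to check it: the null rate, the alternative rate, the number of subjects, alpha, its sidedness and, from the neighbouring sections, the test. Those inputs give a clearly different power. A reader who checks the figure cannot tell whether the rate, the power, the alpha or the method is the wrong item. The stake is the accuracy of a stated operating characteristic for a primary endpoint, and whether the sample size section describes the same test as the analysis section. The size of the trial is not at stake.

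**Working it through.** **Inputs**

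- Null rate p0 = 0.56, fixed (10.6.1, 10.6.3)
- Alternative rate p1 = 0.31 (10.6.2)
- n = 50 (10.6.2)
- One-sided alpha = 0.025 (10.6.1, 10.6.2, 10.6.3)
- Test: one-sample exact binomial (10.6.1, 10.6.3)

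**Step 1: attempt to reproduce the stated 81%.** The test rejects when the number of MAEs, X, is at most c. Here c is the largest integer for which P(X ≤ c | n = 50, p = 0.56) < 0.025.

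| c | P(X ≤ c given 0.56) | P(X ≤ c given 0.31) |
|---|---|---|
| 19 | 0.0079 | 0.888 |
| 20 | 0.0166 | 0.934 |
| 21 | 0.0325 | 0.964 |

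The value 21 exceeds 0.025, so c = 20 and the actual alpha is 0.0166. Power = P(X ≤ 20 | n = 50, p = 0.31) = 93.4%. The stated figure is not reproduced: 93.4 − 81 = 12.4 points.

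The tail sum printed in 10.6.3 starts at k = 1 rather than 0. This has no bearing here, because P(X = 0 | 50, 0.56) is about 1.5 × 10⁻¹⁸.

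**Step 2: does another calculation from the stated inputs give 81%?**

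- One-sample normal approximation, null variance for the critical value and alternative variance for power: standard errors are √(0.56 × 0.44/50) = 0.0702 and √(0.31 × 0.69/50) = 0.0654. Power = Φ((0.25 − 1.96 × 0.0702)/0.0654) = Φ(1.72) = 95.7%. Across the usual choices of variance and continuity correction, the range is 92.8% to 96.9%.
- One-sample arcsine approximation: 95.0%.
- Exact test on 44 evaluable subjects (50 × 0.88, using the 12% drop-out of 10.7.2): rejects at 17 or fewer, power 89.4%.
- Exact test at alpha 0.0125: rejects at 19 or fewer, power 88.8%.
- Two-sample comparison with 50 per arm, one-sided 0.025: 71.9% pooled, 74.1% unpooled, 66.4% by Fisher's exact test.

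None is within 2 points of 81%.

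**Step 3: what would give about 81%?** Each route found needs an input that the plan does not state for this test:

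| Changed input | Power |
|---|---|
| Exact test, true rate 35% instead of 31% | 81.4% |
| Exact test, null of 51% or 52% instead of 56% | 82.1% |
| Exact test, alpha 0.005 | 82.1% |
| Two-sample pooled normal test, 50 per arm, one-sided 0.05 | 81.7% |
| Two-sample pooled normal test, one-sided 0.025, 50 treated against an assumed 80 controls | 80.5% |

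**Step 4: consequence for the trial.** Exact test at p1 = 0.31, one-sided 0.025:

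| n | Rejects at | Actual alpha | Power |
|---|---|---|---|
| 50 | 20 or fewer | 0.0166 | 93.4% |
| 132 | 62 or fewer | 0.0230 | above 99.9% |
| 150 | 71 or fewer | 0.0202 | above 99.9% |

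**The case against.** The strongest reply is that nothing depends on the figure. Fifty is not the trial's sample size, and 31% is not the planning rate; the sentence is a what-if. Effectiveness sets the size, and the larger-of-two comparison in 10.7.2 would come out the same whatever safety number is used. The stated power is also too low rather than too high, so it misleads in the safe direction. All of this stands, and it is why the point is minor. It does not make the figure right: a 12-point gap is too wide for the word approximately to cover.

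Three stronger readings are tempting, and the documents support none of them.

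- A reader might infer that the safety endpoint is underpowered or the trial wrongly sized. Step 4 shows the opposite.
- A reader might count it as a second error that 10.6.2 prints no number for the 16.6% rate. That is only missing detail. The inputs are given, and the description is correct: the smallest number with at least 80% exact power is 13 (rejects at 3 or fewer, actual alpha 0.0170, power 84.4%).
- A reader might infer that 31% is a misprint for 35%, or that a two-sample calculation was carried over; 10.6.2 does use a control-style symbol for the 56%. Several different changes give a value near 81%, as step 3 shows, and the documents do not say which, if any, was made.

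**Conclusion.** The stated power is wrong as written. Under the one-sample exact binomial test of 10.6.1 and 10.6.3 (null 56%, one-sided alpha 0.025), 50 subjects give 93.4% power at a 31% MAE rate, not approximately 81%: an understatement of about 12 points. This takes all 50 subjects as evaluable at 30 days. Allowing 12% drop-out gives 89.4%, which still does not match.

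The error is conservative and its practical effect is nil. The trial size, the alpha, the planned analysis and the conclusions it can support are unchanged. How the 81% arose cannot be determined from the documents.

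**What to change.** Change the sentence in 10.6.2 to say that, at a 31% MAE rate, 50 subjects give about 93% power (exact binomial, one-sided 0.025). If a different method or input lay behind the 81%, the sponsor should state it and make it consistent with the single-arm exact test in 10.6.1 and 10.6.3.

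If the sponsor would rather quote the smallest number giving 80% power at 31%, note that exact power does not rise smoothly with n: it is 80.5% at 33, 77.0% at 34 and 83.4% at 35, and stays at or above 80% only from 35.

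The cost is one sentence. Sample size, analysis and conduct are unaffected.

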10.6.3 Analysis Plan

All subjects who receive treatment will be included in the safety analysis.

A univariate test will be done with the exact binomial distribution to determine if the frequency of MAE in the study population is statistically significantly less than 0.56. The formula for this test is provided below.

$$P(X \leq x_t | 0.56) = \sum_{k=1}^{x_t} \binom{n_t}{k} 0.56^k 0.44^{n_t-k} < 0.025$$

Where x_t is the number of study subjects experiencing an MAE and n_t is the number of subjects in the study. If the above expression holds for the observed x_t , the null hypothesis will be rejected and the alternative hypothesis will be accepted.

If there is heterogeneity among the study sites in MAE response, the analysis will be done by the method of Fleiss (1993). The test statistic will be given by the following formula.

$$z = \frac{(\bar{p}_T - 0.56)}{SE(\bar{p}_T)}$$

Where the formula for the weighted estimate of the proportion is given by the following:

$$\bar{p}_T = \frac{\sum_k W_k p_{Tk}}{\sum_k W_k}$$

And the formula for the weight in site k is given by the following:

$$W_k = \left(\frac{1}{n_k} p_k (1 - p_k) \right)^{-1}$$

And the formula for the standard error is given by the following:

$$SE(\bar{p}_T) = \left(\sum_{k=1}^{m_T} W_{Tk} \right)^{-1/2}$$

If the z has a P-value less than a one-sided alpha of 0.025, the null hypothesis will be rejected and the alternative will be accepted.

To determine those factors that may be associated with MAE, a supportive covariate analyses will be performed by logistic regression to determine if there are differences in the rates among groups when adjusted for other factors in the study population only. Covariates for these analyses will be age, gender, ASA class, cardiac/coronary artery disease (a composite variable to include arrhythmia, CHF, prior MI, CABG/PCI, heart valve repair/replacement), histories of cancer, cerebrovascular accident, coagulopathy, COPD, diabetes, hypertension, liver disease, peripheral arterial occlusive disease, renal failure, smoking, maximum aneurysm diameter, and study site. The final model will be reduced by backward elimination until no covariate terms remain in the model with a P-value less than 0.05.

A descriptive analysis and a Kaplan-Meier analysis of the MAE composite at 30 days will be presented. The descriptive analysis will present the rates for the composite MAEs and each individual adverse event that is part of the composite with corresponding 95% exact confidence intervals.

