5. STUDY POPULATION

5.1. PRIMARY INVESTIGATION

Up to 30 sites in the EU, Canada, and the United States will enroll up to 180 subjects including 30 Roll-in subjects and up to 150 patients in the Intention to Treat Pivotal Cohort for endpoint analysis. Total enrollment at a single site is restricted to 15% of the Pivotal Cohort. Following investigator training, each PI will commence patient screening and enrollment under approval per applicable national and local clinical trial requirements* and complete a minimum of one (1) successful Nellix case (Roll-in) in their training phase. This training period may be modified at the discretion of Endologix. Physicians will be directly supervised in each case by designated Endologix staff.

Pivotal Cohort: Up to 150 subjects will be enrolled at a maximum of 30 sites in the US and the EU. This includes the statistically justified sample size of 132 plus an allowance for deviations from assumptions.

Roll-In Cohort: One (1) roll-in subject may be enrolled per site, therefore a maximum of 30 enrolled in the study, to allow for Investigator(s) to receive additional training on the Nellix System. Any roll-in subjects will be screened, consented, treated and followed identically to the main study cohort. However, the roll-in cohort of this study will be evaluated separately.

* Commercially approved clinical trial requirements in the EU (CE Mark), IDE approval in the US, and ITA approval in CA

Confidential. This document and the information contained herein may not be reproduced, used or disclosed without written permission from Endologix, Inc.

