5.2. EXTENDED INVESTIGATION

Sites that participated in the Primary Investigation will be invited to participate in an Extended Investigation after enrollment closure of the primary investigation. This Extended Investigation will permit study site continued access to the Nellix System through the Primary Investigation's completion of the primary safety and effectiveness endpoint, and FDA review of the premarket approval (PMA) Submission. It is estimated that this Extended Investigation (Continued Access) phase will enroll an additional 150 patients.

Continued Access Cohort: Up to 250 patients will be enrolled into the Extended Investigation based on an enrollment rate of 0.5 patients per site per month and an estimated 20 months from the close of enrollment in the Primary Investigation. Enrollment in Extended Investigation (continued access) phase will be limited to the 27 US sites only as the Nellix System is commercially available to the three participating European sites.

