5.4. EXCLUSION CRITERIA

A patient who meets ***none of the following*** criteria potentially ***may be included*** in the study:

1. Life expectancy <2 years as judged by the Investigator;
2. Psychiatric or other condition that may interfere with the study;
3. Participating in another clinical study;
4. Known allergy or contraindication to any device material;
5. Coagulopathy or uncontrolled bleeding disorder;
6. Ruptured, leaking or mycotic aneurysm;
7. Serum creatinine (S-Cr) level >2.0 mg/dL;†
8. CVA or MI within three months of enrollment/treatment;
9. Aneurysmal disease of the descending thoracic aorta;
10. Clinically significant mural thrombus within the proximal landing zone (minimum 10mm) of the infrarenal non-aneurysmal neck (>5mm thickness over >50% circumference);
11. Connective tissue diseases (e.g., Marfan Syndrome);
12. Unsuitable vascular anatomy that may interfere with device introduction or deployment;
13. Pregnant (female of childbearing potential only).

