To determine those factors that may be associated with Treatment Success, covariate analyses will be performed by logistic regression to determine if there are differences in the Treatment Success rates in the study population when adjusted for other factors. Possible covariates eligible for these analyses will be age, gender, ASA class, cardiac/coronary artery disease (a composite variable to include arrhythmia, CHF, prior MI, CABG/PCI, heart valve repair/replacement), cancer, cerebrovascular accident, COPD, diabetes, hypertension, liver disease, peripheral arterial occlusive disease, renal failure, smoking, maximum aneurysm diameter, and study site. Because there are too many possible covariates to include in a model, screening is necessary to reduce the number of eligible covariates for consideration in the final model. Screening logistic regression models to include only the covariate, will be used. If the P -value for the screening model for the covariate is less than 0.20, the covariate will be included in the competition for the final model. The final model will be obtained by manual backward elimination to have the seven or fewer covariates with P -value less than 0.05.

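### The supportive MAE covariate model in 10.6.3 starts elimination from 16 unscreened covariates including study site: up to 44 parameters for about 25 expected events, so finite estimates of the starting model almost certainly do not exist

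*Combined protocol and SAP*

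**What the plan says.** Section 10.6.3 describes a supportive logistic regression to find factors associated with MAE. The list begins "Covariates for these analyses will be age, gender, ASA class, cardiac/coronary artery disease", continues with ten history items (coagulopathy among them), and ends with "maximum aneurysm diameter, and study site". The next step is backward elimination. The section gives no screening step, no limit on model size, no rule for how site enters, and no estimation method other than ordinary logistic regression. Section 10.3 sets SAS defaults wherever nothing else is specified.

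Section 10.7.3 has the same list for Treatment Success, without coagulopathy. It states: "Because there are too many possible covariates to include in a model, screening is necessary". It then screens each covariate alone at P < 0.20 and limits the final model to seven or fewer.

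Section 10.4 allows small sites, generally those with four or fewer subjects, to be combined. That rule is written for the comparison of sites at baseline, and 10.6.3 does not refer to it.

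**The concern.** The plan recognises the problem in one model and not in its twin. Study site is the costly term: as a class variable it takes one parameter fewer than the number of sites, and the pivotal cohort averages only about five subjects per site. A site with no MAE predicts its outcome perfectly, so its coefficient runs off to minus infinity under maximum likelihood. Elimination would then start from a fit whose estimates and standard errors have no meaning for several terms.

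What is at stake is the list of MAE predictors. The synopsis and 10.6.1 promise multivariable analyses of predictors, and this is the only such model specified for MAE. The terms left in it could reflect separation and software defaults more than the data.

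**Working it through.** **Inputs from the documents**
- Subjects and sites (5.1): "Up to 150 subjects will be enrolled at a maximum of 30 sites in the US and the EU". The figure of 30 is supported by 5.2, where continued access "will be limited to the 27 US sites only as the Nellix System is commercially available to the three participating European sites": 27 + 3 = 30.
- The plan's own recruitment figure reproduces: 132 / 0.88 = 150 (10.7.2). For safety, 150 is the right base: 10.6.3 includes all treated subjects, and 10.2 assigns an MAE to anyone lost before 30 days.
- MAE rate (10.6.2): "the rate for the test arm has been increased to 16.6" per cent. Pessimistic case: "Should the Nellix rate be as high as 31" per cent.

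**Covariate count.** Age, gender, ASA class and cardiac disease (4); cancer, cerebrovascular accident, coagulopathy, COPD, diabetes, hypertension, liver disease, peripheral arterial disease, renal failure and smoking (10); aneurysm diameter and study site (2). Total 4 + 10 + 2 = 16.

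**Parameters.** 15 single-parameter terms + (30 − 1) site indicators = 44, not counting the intercept. This takes ASA class as one term and assumes no pooling of sites.

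**Events per parameter**

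| MAE rate | Expected MAEs | With site (44) | Without site (15) |
|---|---|---|---|
| 16.6% | 150 × 0.166 = 24.9 | 0.57 | 1.7 |
| 31% | 150 × 0.31 = 46.5 | 1.06 | 3.1 |

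**Event-free sites**, at 150 / 30 = 5 subjects per site:
- At 16.6%: 0.834^5 = 0.403 per site, so 30 × 0.403 = 12.1 sites. Chance that no site is event-free: (1 − 0.403)^30, about 2 in 10 million.
- At 31%: 0.69^5 = 0.156 per site, so 4.7 sites. Chance that no site is event-free: (1 − 0.156)^30 = 0.6%.

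**Simulation.** A linear-programming check asked whether a finite maximum-likelihood estimate exists, in 400 simulated trials per scenario. Covariate prevalences had to be assumed because the documents give none.

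| Starting model | 16.6% | 31% |
|---|---|---|
| 30 equal sites, 44 parameters | none exists in 100% | none in 99.8% |
| Unequal sites, small ones pooled as in 10.4, about 29 parameters | none in about 99% | none in about 72% |
| Site left out, 15 parameters | none in about 68% | none in about 33% (separate run of 300) |

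The last row depends on the assumed rare binary covariates (for example coagulopathy at 3%). It shows that removing site does not settle the matter alone.

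**The case against.** **The model is only supportive.** This stands. Primary safety is the exact binomial test against 56%, and 10.5 handles site differences separately. No success criterion uses this model.

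**The model could still be run.** A reader might infer that the fit will fail to converge or that elimination cannot proceed. That goes too far. The problem is mainly quasi-separation: some coefficients diverge while the likelihood settles. Complete separation occurred in under 1% of 300 simulated trials at 16.6% and in none at 31%. Software would often print a fit, and site might well be eliminated. But it would leave on the strength of a P-value that carries little information, and the other terms are judged alongside it until then.

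**44 is an upper bound.** This also stands. Thirty is a maximum, enrolment will be unequal, and 10.4 might be read as allowing pooling. Pooling is not invoked in 10.6.3, however, and at 16.6% it cures almost nothing.

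**Coagulopathy.** A reader might infer that it cannot occur, because exclusion 5 is "Coagulopathy or uncontrolled bleeding disorder". The covariate appears among histories, so a past or corrected disorder might be eligible. Rare is a fair expectation; impossible is not established.

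**The effectiveness model.** A reader might extend the criticism to 10.7.3: 132 × 12% = 15.8 failures against seven terms is 2.3 per term. But seven is a ceiling after screening, and 132 × 20% = 26.4 failures would occur at the performance goal. A cap of one term per ten events is a debatable rule of thumb; it would leave about one effectiveness term, against the multivariable intent in 10.7.1. The point here does not need it.

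**Conclusion.** The point holds for the starting model in 10.6.3. With site as a fixed class effect and no screening, there are up to 44 parameters for about 25 expected MAEs (0.6 events each), or about 47 at 31% (1.1 each). Finite maximum-likelihood estimates almost certainly do not exist at either rate unless sites are pooled, and pooling helps only in part.

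This rests on about 30 sites of about five subjects, ASA class as one term, and the plan's two MAE rates. Only the simulation percentages depend on assumed covariate prevalences; the event-free-site arithmetic does not.

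A reader might infer that the trial's safety conclusion is in doubt. The documents do not support that: the primary test does not use this model. The consequence is an unreliable list of MAE predictors, which should be corrected before analysis.

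**What to change.** In 10.6.3:
1. Remove study site from the fixed covariates and leave site differences to the exact homogeneity test in 10.5, which tolerates event-free sites.
2. Apply the single-covariate screen of 10.7.3 (P < 0.20) before backward elimination.
3. Fit by Firth penalised likelihood, so that rare binary covariates such as a history of coagulopathy do not give infinite estimates. At the least, drop coagulopathy, as 10.7.3 does.
4. Correct the elimination sentence in the same edit. As worded, it removes terms with P below 0.05 and keeps the rest. Correcting that sentence alone would not cure the problem above.
5. Label the resulting predictors exploratory.

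No fixed events-per-term cap is needed, and 10.7.3 can keep its ceiling of seven.

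The cost is a few lines of SAP text and a standard estimation option. The downside is that predictor estimates are not adjusted for site and fewer predictors may be named.

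### The stopping rule for the supportive MAE model in 10.6.3 is worded in reverse: no covariate with P < 0.05 can remain in the final model

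*Combined protocol and SAP*

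**What the plan says.** The covariate paragraph of section 10.6.3 opens with its aim: "To determine those factors that may be associated with MAE, a supportive covariate analyses will be performed by logistic regression". It lists 16 covariates, the last being study site, and closes with the selection rule: "The final model will be reduced by backward elimination until no covariate terms remain in the model with a P-value less than 0.05". It does not say which term leaves at each step.

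Section 10.7.3 describes the corresponding model for Treatment Success. There, covariates are first screened one at a time at P < 0.20, and the final model is reached by "manual backward elimination to have the seven or fewer covariates with P -value less than 0.05".

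Section 10.6.1 gives the role of such models on the safety side: "Multivariable analyses will be used to assess predictors of success". The synopsis repeats that commitment. No other section restates or corrects the rule in 10.6.3. The revision history's one entry under 10.6.3 (Revision 04) concerns only the site-weight equation.

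**The concern.** Backward elimination normally drops weak terms until all survivors meet the significance threshold. The sentence in 10.6.3 sets the opposite end point: the process stops once no survivor meets it. A model meant to identify factors associated with MAE is thereby barred from containing any factor found significant at 0.05.

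What is at stake is the prespecified predictor analysis for the safety endpoint. Section 11.2 makes the biostatistician responsible for reporting according to the analysis plan. Someone who follows the sentence reports a model with no significant predictor in it. Someone who applies the usual rule departs from the written plan at a data-driven step, where prespecification is most useful.

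**Working it through.** There is no stated figure to reproduce. The point follows from the wording.

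**1. The two stopping conditions.** Let S be the covariates currently in the model and p_j(S) the P-value of covariate j in that model.

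- Usual stop: p_j(S) < 0.05 for every j in S.
- Stop as written in 10.6.3: p_j(S) ≥ 0.05 for every j in S.

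The only model that satisfies both is the one with no covariates.

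**2. What the written stop produces.** Because the removal order is not given, there are three cases.

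| Situation | Result under the written stop |
|---|---|
| No term in the full model has P < 0.05 | Stops at once; all 16 covariates stay, none significant |
| Some term has P < 0.05, and such terms are the ones removed | Significant predictors go; non-significant terms stay |
| Some term has P < 0.05, and the largest P is removed first | Non-significant terms go, the stop is still not met, and removal continues into the significant terms; normally ends empty |

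In the third case the process stops short of empty only if removing one term happens to make all the others non-significant. In no case does a covariate with P < 0.05 reach the final model.

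**3. The two sections side by side.** In 10.7.3 the covariates with P < 0.05 are the ones kept. In 10.6.3 they are the ones that may not remain. The threshold is the same and the method has the same name, but the direction is opposite, and the plan gives no reason for a difference.

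**4. Illustration (assumed settings).** 300 simulated data sets were run with 150 subjects, 10 independent standard normal covariates (2 true predictors with log-odds 1.0 per SD, 8 with no effect) and intercept -1.9. The number of covariates, their distribution, the effect sizes and the intercept are assumptions, not figures from the plan.

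| Rule | True predictors kept (of 2) | Null covariates kept (of 8) | Empty models |
|---|---|---|---|
| Usual rule, largest P out first | 1.96 | 0.37 | 0 of 300 |
| Written stop, smallest P out first | 0.06 | 7.62 | 0 of 300 |
| Written stop, largest P out first | 0 | 0 | 300 of 300 |

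The kept columns are averages over the 300 runs. The table shows the direction of the effect only.

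**5. How far the illustration is from this trial.** Section 10.6.3 lists 16 covariates, and study site alone could have up to 30 levels before the pooling of small sites described in 10.4. At the planning rate of 16.6% in 10.6.2, 150 subjects give 150 × 0.166 = 24.9, about 25 MAEs. The retention figures above should not be read as forecasts for the real model under either wording.

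**The case against.** The strongest reply is that this is an obvious slip in a secondary analysis. The paragraph calls the analysis supportive, names a standard technique and states its aim, and 10.7.3 shows the intended direction. A competent statistician would very probably notice and run the usual procedure. All of that stands, and it limits the consequence. It does not make the sentence usable, since the sentence cannot be followed and still meet its stated aim. The sponsor has treated a similar slip as worth correcting: Revision 04 of the protocol reversed the direction of the heterogeneity P-value criterion and gave a typographical error as the reason.

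A reader might be tempted by three stronger readings that the documents do not support.

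- *The rule deletes the real predictors and keeps the noise.* That needs significant terms to be the ones removed, and the plan never says so. With the usual removal order the model is normally emptied and no noise is kept.
- *Sections 10.6.3 and 10.7.3 give conflicting instructions.* They govern different models, and 10.7.3 also has a screening step and a cap of seven covariates. Section 10.7.3 is good evidence of intent, not a rival rule for the MAE model.
- *The safety conclusion is at risk.* The primary test is an exact one-tailed binomial test against 56%, and the fallback for heterogeneous sites is a weighted z-test. Neither uses the covariate model.

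**Conclusion.** The stopping condition in 10.6.3 is reversed. As written, no covariate with P < 0.05 can be in the final MAE model, so the analysis cannot do what its own paragraph asks. This rests on the wording alone and needs no assumption about effect sizes, event rates or removal order. The removal order decides only the form of the failure: predictors lost, or the model emptied.

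Severity is minor to moderate. The primary safety test, its alpha, the sample size, the analysis populations and the handling of missing data are untouched, and no success criterion depends on this model. The simulation figures are illustrative and the conclusion does not need them.

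Correcting the direction does not guarantee a stable model. Starting from 16 covariates including site, with about 25 expected events, the full model may be hard to fit under either wording.

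**What to change.** Replace the last sentence of the covariate paragraph in 10.6.3 with: *Terms will be removed one at a time, largest P-value first, until all covariate terms remaining in the model have a P-value less than 0.05.* The clause on order is worth adding because the current text leaves it open.

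The cost is one sentence in the statistical section, with no change to data collection, sample size or the primary tests. Section 8.6 refers to two-year data from the US IDE trial reported in October 2016, so the 30-day model may already have been fitted. If it has, the report should state which rule was applied and record this as a correction of wording.
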